| | |
|---|--|
| Title | Nerve stimulation's effectiveness at UI frequency in overactive patients in home |
| NCT# | NCT03595215 |
| Objectives | To demonstrate safety and effectiveness of nerve stimulation using the Leo-U TranStim System |
| Indications for Use/Patient Population | Leo-U TranStim System is intended for use in patients suffering overactive bladder (OAB) and associated symptoms of urinary urgency, urinary frequency, and urge incontinence (UI). Subjects will receive treatment sessions of Nerve Stimulation each week for 8 weeks, at home. |
| Trial Design | Single center feasibility, non-randomized, unblinded, Non-Significant Risk (NSR) trial. |
| Number of Subjects | 11 |
| Number of Sites | 1 |
| Inclusion Criteria | 
Candidates must meet ALL of the following:
 
 1. Females 2. 55-100 years old 3. Have an average urinary frequency of \geq 8 voids per 24 hours (based on a pre-treatment 3-day voiding "training" diary) 4. Have self-reported bladder symptoms of more than 3 months 5. Are ambulatory and able to use the toilet independently 6. Have been off antimuscarinics, anticholinergics or beta-3 agonists for at least 2 weeks prior to enrollment OR on a stable dose for the prior 3 months 7. Patient has urinary urge incontinence of \geq 8 episodes from a 3-day diary (with incontinence associated at urge level moderate or severe) 8. Able to provide informed consent 9. Capable and willing to follow all study-related procedures |
| Exclusion Criteria | 
Candidates cannot meet ANY of the following:
 
 1. Have primary complaint of stress urinary incontinence 2. Have a pacemaker or implantable defibrillator 3. Had botox injections in the bladder or pelvic floor muscles in the past 12 months 4. Have a current urinary tract or vaginal infection 5. Have an active implantable SNS device (InterStim & Bion) 6. Have been diagnosed with peripheral neuropathy or nerve damage 7. Currently pregnant 8. Deemed unsuitable for enrollment in study by the investigator based on subjects' history or physical examination |

| | |
|--------------------------------|--|
| Procedures | 
 1. Subjects will sign the Informed Consent and be screened for eligibility in the study. Subjects will receive receive the voiding diaries and questionnaires, which will be completed at home. 2. Subjects will complete "training" voiding diary. 3. Subjects will complete another 3-day voiding diary and an OAB-q to establish a baseline. 4. Once questionnaires are complete, subjects will visit the site, and receive instructions on how to use the TranStim device. 5. Subjects will bring the TranStim device with them for in-home use. For 8 weeks, subjects will self-administer minutes of TranStim therapy. The patient will fill out voiding diary and an OAB-q at the start of their 5th and 8th week of treatment. 6. Subjects will return to the clinic at the after their 8th treatment week to determine if there are any SAEs or UADEs. Subjects will return study related materials to the site during this last visit. |
| Endpoints | 
Efficacy Endpoints (following Leo-U TranStim therapy):
 
 1. At least 50% decrease in the number of UI episodes compared to pre-treatment 2. At least 20% decrease in micturitions per day compared to pre-treatment 3. At least 15% improvement in incontinence QoL scores compared to pre-treatment 
Primary Safety Endpoint The incidence and severity of Adverse Events (AEs) including device and procedure-related AEs. The incidence and severity of SAEs (regardless of relationship to device or procedure). Primary safety endpoints will be evaluated at follow-up visit.
 |
| Safety | Adverse Events (both expected and unexpected) will be recorded and reported appropriately throughout the study. |
| Sample Size Calculation | This is an open-label feasibility study with the goal of providing proof of-principle data for TranStim. Therefore, we will be evaluating the results for trends that support further investigation. Nonetheless, by having each subject serve as her own control, using a repeated measures ANOVA, a sample size of 10 will provide sufficient power to detect an effect size of 0.7 ($\alpha=0.05$, power=0.80). Eleven subjects will be enrolled to account for a 10% drop-out rate. |

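### Does inclusion item 7, which names no diary, let the baseline diary decide entry and so build in a spurious fall in UI episodes?

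*Combined protocol and SAP*

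**What the plan says.** All the relevant text is in the synopsis table of the combined protocol and SAP.

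- **Inclusion Criteria, item 3** sets the voiding-frequency threshold and names its source: "based on a pre-treatment 3-day voiding 'training' diary".
- **Inclusion Criteria, item 7** sets the incontinence threshold, at least "8 episodes from a 3-day diary (with incontinence associated at urge level moderate or severe", and does not name its source.
- **Procedures, step 1:** "Subjects will sign the Informed Consent and be screened for eligibility in the study". In the same step women "receive the voiding diaries and questionnaires, which will be completed at home".
- **Procedures, step 2:** the training diary is kept.
- **Procedures, step 3:** "Subjects will complete another 3-day voiding diary and an OAB-q to establish a baseline".
- **Procedures, step 4:** "Once questionnaires are complete, subjects will visit the site, and receive instructions on how to use the TranStim device". No eligibility review is mentioned here or later.
- **Endpoints, efficacy item 1:** "At least 50% decrease in the number of UI episodes compared to pre-treatment". The pre-treatment measurement is not defined further.
- **Trial Design and Sample Size Calculation:** one unblinded arm of 11 women, each her own control, with results to be examined for trends.

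**The concern.** Two 3-day diaries precede treatment, and item 7 fits either. Read literally, the procedures place screening where neither diary exists, and the next listed visit comes when both do. A woman with 6 episodes and then 9 could be admitted on the second count, and 9 would then be her reference.

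A count that must reach 8 to admit a woman is selected upward, so a later count tends to be lower even if the device does nothing. In a single-arm before-after study that fall is added to any treatment effect and cannot be separated from it. At stake is an inflated result on the UI endpoint.

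**Working it through.** **1. What the text assigns to each diary**

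| Diary | Use the plan states |
|---|---|
| Training (step 2) | Entry, through item 3 |
| Second 3-day diary (step 3) | Baseline, with the only pre-treatment OAB-q |

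Item 3 cannot be judged until the training diary is back, and that diary is handed out in step 1. Eligibility therefore cannot close at step 1, which is better read as the start of screening. What the list omits is a line saying when the diary results are reviewed. Item 7 stands in the same list as item 3 and needs the same kind of record. Counting both on the training diary is the reading that fits every stated use.

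**2. Size of the bias under each reading**

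The plan gives no distribution of diary counts, so there is no figure of its own to reproduce. The inputs are assumptions: true 3-day counts gamma-distributed with mean 8, 10 or 12 and CV 0.5, 0.6 or 0.7; diary variance 1 or 1.5 times its mean; no treatment effect. That makes 18 scenarios of 1,000,000 simulated women each.

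Let T be the training count, B the step 3 count and F one later count. Spurious fall = 1 − mean(F)/mean(B). A chance responder has F ≤ 0.5 × B. Excess is measured against entry on T within the same scenario.

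| Entry decided on (reference B) | Spurious fall | Chance responders | Excess | Excess × 11 women |
|---|---|---|---|---|
| T ≥ 8 | −0.1% to 0.1% | 5.6-13.6% | none | none |
| T ≥ 8 or B ≥ 8 | 1.7-6.7% | 7.7-18.2% | 1.8-4.7 points | 0.2-0.5 |
| B ≥ 8 | 4.2-15.1% | 8.1-21.6% | 2.3-8.0 points | 0.3-0.9 |

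Of women with 8 or more on at least one diary, 24.3-49.2% have it on only one: 11 × 0.243 = 2.7 to 11 × 0.492 = 5.4 women. So the choice of reading can affect who enters, but the endpoint moves little.

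**3. Wider assumptions**

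A second set used means of 6 to 12, CV 0.4 or 0.6, and either Poisson counts or counts with variance μ + μ²/8. It compared entry on B with entry on T.

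- Mean 10, CV 0.6, Poisson. Entry on B: 14.20 falls to 13.28, and 1 − 13.28/14.20 = 6.5%. Entry on T: 13.29 stays at 13.29. Responders 10.3% against 6.9%, so 11 × 0.034 = 0.4 woman.
- Most adverse: mean 6, CV 0.4, overdispersed. Entry on B: 11.13 falls to 7.75, and 1 − 7.75/11.13 = 30.4%. Entry on T: 7.75 stays at 7.75. Responders 38.0% against 21.1%, so 11 × 0.169 = 1.9 women.

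Across this set the fall is 4.5-30.4% with entry on B and within 0.2% of zero with entry on T. The either-diary rule was not run here. Its fall must be smaller than that for entry on B alone, because the women it adds have B below 8 and on average show a rise.

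**4. Against the 50% target**

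If the endpoint is read as a group mean and the device effect is proportional, a spurious fall of 2% or 7% means a true fall of 1 − 0.50/0.98 = 49% or 1 − 0.50/0.93 = 46% would show as 50%.

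**The case for a change.** The strongest case for acting is that the authors named the diary in item 3 and not in item 7, that no step tells the site when to check either criterion, and that no sentence bars the step 3 diary from deciding entry. The stated objective is to demonstrate effectiveness, and without a control arm the bias, if present, always favours the device. In the most adverse assumed scenario, entry and baseline on the same diary give a spurious standardized change of 0.66, close to the 0.7 in the Sample Size Calculation (whose type of effect size is not stated). The remedy would cost a few words.

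The silence in item 7 and the missing review step are real, and the direction of the bias is certain if one diary serves both purposes. But the 0.66 needs three things together: entry judged at step 4, the step 3 diary alone allowed to admit, and that same diary used as reference. The plan directs neither of the first two, and the second goes further than item 7's open wording. With entry on the training diary the standardized change is 0.00 in the same scenario. The 9-then-6 woman is no counter-example: admitted on the training diary with 6 as reference, she follows the unbiased route. Extra wording would mostly record a separation that the two-diary sequence already implies.

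**Conclusion.** No change follows. Item 7 leaves a detail unstated that item 3 and step 3 together supply: training diary for entry, step 3 diary and OAB-q as the pre-treatment reference. On that reading the spurious fall is 0%. If a site let either diary admit, the expected distortion is a fall of about 2-7% and 0.2-0.5 woman of 11, in an open-label feasibility study that looks for trends and states no responder rate to be met.

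The sizes rest on assumed count distributions, and the upper figures (up to a 30.4% fall and 1.9 women) apply only if the baseline diary alone decided entry. The 0% assumes that a woman's diaries vary independently around a stable underlying rate. If the two pre-treatment diaries fell in the same bad spell, some regression to the mean would remain, and naming the diary in item 7 would not remove it.

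### The last visit is set to look for SAEs and UADEs, while the primary safety endpoint counts all AEs, and no listed step asks about the rest

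*Combined protocol and SAP*

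**What the plan says.** Everything relevant is in the synopsis table.

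- **Endpoints, Primary Safety Endpoint.** There are two components: "The incidence and severity of Adverse Events (AEs) including device and procedure-related AEs", and "The incidence and severity of SAEs (regardless of relationship to device or procedure". On timing: "Primary safety endpoints will be evaluated at follow-up visit".
- **Safety row.** "Adverse Events (both expected and unexpected) will be recorded and reported appropriately throughout the study".
- **Procedures, step 4.** The visit before home use is for training: "Once questionnaires are complete, subjects will visit the site, and receive instructions on how to use the TranStim device".
- **Procedures, step 5.** During the 8 weeks at home: "The patient will fill out voiding diary and an OAB-q at the start of their 5th and 8th week of treatment".
- **Procedures, step 6.** "Subjects will return to the clinic at the after their 8th treatment week to determine if there are any SAEs or UADEs". This is the closing contact: "Subjects will return study related materials to the site during this last visit".

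The synopsis does not spell out UADE, and it does not say which visit the Endpoints row means by follow-up.

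**The concern.** Safety is named in the Objectives row, and the safety endpoint is the only one labelled primary. An AE incidence depends heavily on what subjects are asked. If the site takes its questions from step 6, it asks about serious events and unanticipated device effects. Milder, expected events, including those caused by the device, belong to the endpoint but would enter the record only if a subject volunteered them.

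The setting adds to the risk. Treatment is self-administered at home, so the synopsis describes no staff observation of sessions. A low AE count could then mean that few events happened, or that few were asked about.

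**Working it through.** The plan states no figure on this point, so there is none to reproduce. The check compares the passages, with one line of arithmetic for scale.

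**1. Scope of each row**

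| Place | Events covered | How they are obtained |
|---|---|---|
| Primary Safety Endpoint | All AEs, plus SAEs whatever their cause | Evaluated at the follow-up visit; no method given |
| Safety row | All AEs, expected or not, for the whole study | Recorded and reported; no question, form or contact named |
| Step 6 | SAEs or UADEs | Clinic visit after week 8 |

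**2. Is step 6 narrower?** Read UADE as unanticipated adverse device effect (assumption). An event that is both non-serious and anticipated is then neither an SAE nor a UADE. It is still an AE, so it counts toward the endpoint. Step 6 therefore names a subset of what the endpoint counts.

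**3. Is step 6 the visit at which the endpoint is evaluated?** The text does not say so. It is the only visit listed after home use starts, and it is called the last one. Treating the two as the same is a reasonable inference (assumption).

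**4. Does another step fill the gap?**
- Steps 1 to 3: consent, screening, training diary, baseline diary and OAB-q. No AE question.
- Step 4: device instruction. No AE question.
- Step 5: voiding diary and OAB-q in weeks 5 and 8. No AE question is listed.
- Step 6: the only step that mentions adverse events at all, with the scope shown above.

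No listed step elicits non-serious, anticipated AEs, either while subjects are at home or afterwards.

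**5. Scale.** The documents give no AE rates and no reporting probabilities, so the size of any under-count cannot be derived. What can be shown is how much one subject weighs. If incidence is the share of subjects with at least one AE, missing one affected subject changes it by 1/n:
- n = 11 (all enrolled): 1/11 = 0.0909, or 9.1 percentage points.
- n = 10 (the evaluable number in the sample size row): 1/10 = 0.100, or 10.0 percentage points.

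This is the weight of one subject in a small trial, not an estimate of bias.

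**The case against.** The strongest reply is that the plan already covers this. The Endpoints row assigns the whole endpoint, all AEs included, to the follow-up visit, and the Safety row commits to recording every AE for the whole study. A site that reads the full table is told to record them all, and step 6 contains no word that limits the visit to SAEs and UADEs. The document is also a synopsis, where elicitation methods and case report forms may be left out. Finally, this is a non-significant-risk feasibility study of 11 subjects, assessed for trends, with no safety threshold or hypothesis.

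Much of this stands. A reader might infer that the plan excludes non-serious AEs, or that step 6 contradicts the endpoint. The documents do not support that: the intent to record all AEs is explicit, and step 6 is less complete than its neighbours rather than opposed to them. Nor can it be inferred that the site has no AE procedure, since only the synopsis is available. It would also go too far to say that the final report could not be interpreted, because a report can state how AEs were elicited.

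What remains is practical. A commitment to record does not say who asks, when or how. The one step that does describe safety collection is narrower than the endpoint it serves. Stating the elicitation method in the report would disclose the narrow questioning but would not recover events that were never asked about.

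**Conclusion.** The concern holds as possible under-ascertainment. Step 6 is narrower than the primary safety endpoint, and no step in this synopsis elicits non-serious, anticipated AEs during or after home treatment. This rests on the two assumptions set out above, about the meaning of UADE and the identity of the follow-up visit.

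A reader might take the 9.1 points as the expected error in the AE rate. It is not: it is the effect of one missed subject out of 11, and whether any subject would be missed is unknown.

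The change should be made because the gap touches the only endpoint labelled primary and is cheap to close. Confidence is medium, since a fuller protocol might contain an AE procedure. Even then, step 6 would need to be aligned with the Endpoints and Safety rows.

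**What to change.** 1. **Reword step 6** to match the other two rows. Suggested text: *After the 8th treatment week, subjects attend the clinic, where site staff ask about and record all AEs since consent, including SAEs and UADEs, with severity and relationship to device or procedure.* Counting from consent, rather than from first device use, matches the Safety row, which covers the whole study and so includes the baseline period.
2. **Add one open AE question** to the diary and OAB-q packet already completed in weeks 5 and 8, and list it in step 5. This shortens recall compared with asking for the first time at the last visit. If the forms come back with the other study materials at that visit, the question does not give the site earlier notice of events.
3. **Spell out UADE**, and say that the follow-up visit in the Endpoints row is the step 6 visit, if that is what is meant.

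Cost: a sentence in step 6, a line in step 5, one question asked twice, and a check that the form used at the last visit matches. No extra visit is needed. The downsides are slight form burden and a possibly higher reported AE rate, since solicited events tend to exceed volunteered ones.

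### The only efficacy method named, a repeated measures ANOVA, comes with no missing-diary rule, no outcome scale and no link to the percentage thresholds; an available-data model on a proportional scale would serve an 11-subject trial better

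*Combined protocol and SAP*

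**What the plan says.** - **Method.** The Sample Size Calculation row is the only place where an efficacy analysis is named: "using a repeated measures ANOVA, a sample size of 10 will provide sufficient power to detect an effect size of 0.7", at alpha 0.05 and power 0.80. Each woman is her own control. The row does not give the outcome variable, its scale, the type of ANOVA or the handling of incomplete subjects.
- **Drop-out.** The same row adds: "Eleven subjects will be enrolled to account for a 10% drop-out rate".
- **Data.** Procedures item 3 sets a baseline diary and OAB-q. Item 5 sets the on-treatment measurements, made at home: "The patient will fill out voiding diary and an OAB-q at the start of their 5th and 8th week of treatment". That makes three time points. Item 4 places the device visit after the questionnaires are complete.
- **Endpoints.** The Endpoints row gives three percentage thresholds against pre-treatment. The first is "At least 50% decrease in the number of UI episodes compared to pre-treatment"; the others are 20% for micturitions per day and 15% for quality of life. The row does not say whether they apply to each subject or to the group mean, and no analysis of them is described.
- **Purpose.** The trial is called an open-label feasibility study whose results will be read for trends. The Objectives row nevertheless speaks of demonstrating effectiveness.

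**The concern.** A conventional repeated measures ANOVA needs every visit from every subject. A woman who misses the week-5 diary would be left out even though her baseline and week-8 diaries are in hand. With 11 subjects and an allowance for one loss, a second incomplete subject takes the analysis below the planned size.

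The test also compares mean levels, so it measures additive change, while the endpoints are proportional. The test that is powered is therefore not the analysis that would answer the stated endpoints.

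Finally, no denominator is fixed for the thresholds. One subject is 1/11, or 9 percentage points, of a responder rate. Choosing the denominator after the data are seen could move the headline figure materially.

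**Working it through.** **1. The plan's own sample size.** Inputs from the Sample Size Calculation row: n = 10, effect size 0.7, alpha 0.05, power 0.80. The effect-size metric, number of measurements m, correlation ρ and sidedness are not given, so they are assumed here. For a one-group within-subject ANOVA, λ = f²·n·m/(1−ρ), with degrees of freedom m−1 and (n−1)(m−1).

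| Reading of 0.7 | λ at n = 10 | Power at n = 10 | N for 80% |
|---|---|---|---|
| f = 0.7, m = 2, ρ = 0 | 0.49×20/1 = 9.8 | 0.795 | 11 |
| f = 0.7, m = 3, ρ = 0 | 0.49×30/1 = 14.7 | 0.893 | 9 |
| d = 0.7 (f = 0.35), m = 3, ρ = 0.7 | 0.1225×30/0.3 = 12.25 | 0.828 | 10 |
| d = 0.7 (f = 0.35), m = 3, ρ = 0.5 | 0.1225×30/0.5 = 7.35 | 0.600 | 15 |
| paired dz = 0.7, two-sided t test | – | 0.506 | 19 |
| paired dz = 0.7, one-sided t test | – | 0.655 | 15 |

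The stated 10 is reached or nearly reached under the first three readings and not under the others. It is neither confirmed nor refuted.

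Drop-out: 10×1.1 = 11, and 11×0.9 = 9.9. Division gives 10/0.9 = 11.1, which rounds up to 12, so 11 is within rounding.

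**2. Complete subjects under the conventional method.** On the natural reading of Procedures items 3 and 4, a treated subject already has her baseline, so two diaries are at risk. If each is missing independently with probability p (assumed), the chance that a subject is complete is q = (1−p)². The expected number complete is 11q, and P(fewer than 10) = 1 − 11q¹⁰(1−q) − q¹¹.

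| p | q | Expected complete of 11 | P(fewer than 10) |
|---|---|---|---|
| 5% | 0.9025 | 9.9 | 29% |
| 10% | 0.81 | 8.9 | 65% |
| 20% | 0.64 | 7.0 | 95% |

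The 5% row loses 1 − 0.9025 = 9.75% of subjects, which is about the plan's own 10% allowance. The lower rows go beyond it.

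**3. What each lost subject costs.** Under d = 0.7, m = 3, ρ = 0.7 (the third reading above), power is 0.870 at n = 11, 0.828 at 10, 0.775 at 9, 0.710 at 8 and 0.631 at 7. One loss is covered; the second takes power below 80%.

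**4. What an available-data model recovers.** Assumptions: 11 enrolled, three visits, a drop of 0.7 SD at both on-treatment visits (f = 0.7×√2/3 = 0.33, slightly below the 0.35 of step 3), and on-treatment diaries missing completely at random. The comparison is by simulation, 4,000 runs per setting, so the standard error of each power is at most √(0.25/4000) = 0.008. The available-data model has subject and visit effects and stands in for a mixed model.

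| Missing per diary | ρ = 0.5: complete cases / all data | ρ = 0.7: complete cases / all data |
|---|---|---|
| none | 0.60 / 0.60 | 0.83 / 0.83 |
| 5% | 0.53 / 0.57 | 0.78 / 0.82 |
| 10% | 0.49 / 0.56 | 0.71 / 0.80 |
| 20% | 0.38 / 0.53 | 0.57 / 0.74 |

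The gain is 4 points at 5%, 7 to 9 at 10% and 15 to 17 at 20%. A separate run of the comparison gave 3 to 4, 8 and 16 to 19. Together: roughly 3 to 9 points at 5–10% missing and 15 to 19 at 20%.

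**5. Scale.** Inclusion criterion 7 sets a minimum of 8 UI episodes per 3-day diary and no maximum. A subject who goes from 8 to 4 and one who goes from 16 to 8 both just meet the 50% threshold. They contribute 4 and 8 to an additive mean change. On log(count + 0.5) they contribute ratios of 4.5/8.5 = 0.53 and 8.5/16.5 = 0.52, which are nearly equal.

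**6. Denominator, illustration only.** Suppose 6 of 11 treated subjects respond and 2 non-responders have no final diary. Completers only gives 6/9 = 67%; all treated gives 6/11 = 55%.

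**The case against.** The strongest reply is that this is a gap in specification and not a faulty analysis that the plan has chosen. A reader might infer that the plan commits to raw counts and to discarding every subject with a missing diary. The documents say neither: the variant, the outcome variable and the handling of incomplete subjects are all unstated. That stands, and the point is therefore put conditionally. What remains is that the conventional form has these consequences and nothing in the plan prevents them.

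The plan also allows for one loss. At 5% missing per diary the expected number complete, 9.9, is essentially the planned 10. This stands too; the shortfall is likely only at higher rates, or if missed diaries come on top of drop-out.

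A reader might go on to conclude that a completers-only analysis overstates benefit. That requires missingness related to outcome, which the documents neither state nor exclude. The 67% versus 55% example shows a possible size, not an expected one.

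A firm power advantage for the log scale should not be claimed either. Simulated power on raw counts ran from about 6% to 55% for median final-to-baseline ratios of 0.6 to 0.8, depending on assumed variability. The log scale equalled or beat raw counts to within simulation error, but by an amount set by the assumptions. The case for it is that it estimates the quantity the endpoints describe. Even so, a mean percentage change is not a threshold analysis, so the responder proportions are still needed.

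Lastly, no pass/fail decision rests on the F test in a trend-seeking feasibility study. That lowers the consequence. It does not remove it, given the 80% power claim and the stated objective.

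**Conclusion.** The concern holds in conditional form. The plan names one efficacy method and gives it no outcome scale, no missing-diary rule and no connection to the three percentage thresholds. If the ANOVA is run conventionally, the chance of fewer than 10 complete subjects is 29%, 65% or 95% at 5%, 10% or 20% missing per diary. An available-data model would recover roughly 3 to 9 points of power at 5–10% missing and 15 to 19 points at 20%.

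These figures rest on assumptions that are not in the documents: independent missingness at those rates, baseline always present, and, for power, a 0.7 SD drop with correlation 0.5 to 0.7. Power for the thresholds themselves cannot be computed, because no expected or null responder rate is given. The documents do not support saying that the sample size of 10 is wrong, or that results will favour completers.

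**What to change.** Replace the repeated measures ANOVA with the following wording, settled before the data are examined:

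1. A mixed model for repeated measures that uses every available diary from all treated subjects, with a small-sample degrees-of-freedom method such as Kenward-Roger.
2. UI episodes analysed as log(count + 0.5) and micturitions on the log scale, so that the estimate is a percentage change (approximate for UI, because of the 0.5) with a 95% CI. State the scale for the OAB-q score as well.
3. For each of the 50%, 20% and 15% thresholds, the proportion of subjects meeting it, with all treated subjects in the denominator and a missing final diary or questionnaire counted as threshold not met. This is needed alongside the model, which still assumes that missingness is explained by the observed data.

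A single baseline-to-week-8 contrast is optional, since it can cost power.

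The cost is analysis wording only; no data or visits are added. The one downside is that the responder rate may be slightly lower than a completers-only figure.

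### Does a power figure for an unlabelled effect size of 0.7, tied to none of the three percentage-threshold endpoints, call for a change to the plan?

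*Combined protocol and SAP*

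**What the plan says.** The efficacy part of the Endpoints row lists three criteria, headed as applying after therapy: "At least 50% decrease in the number of UI episodes compared to pre-treatment", "At least 20% decrease in micturitions per day compared to pre-treatment" and "At least 15% improvement in incontinence QoL scores compared to pre-treatment". None is labelled primary. The row does not say whether a threshold applies to each subject or to the group mean.

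The only statistical method named is in the Sample Size Calculation row: "by having each subject serve as her own control, using a repeated measures ANOVA". The same sentence states that "a sample size of 10 will provide sufficient power to detect an effect size of 0.7", with alpha 0.05 and power 0.80, and 11 subjects are enrolled to allow for 10% drop-out. The text before it describes an open-label feasibility study that supplies proof-of-principle data and is evaluated for trends.

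The Procedures row gives a baseline diary and questionnaire. It then says: "The patient will fill out voiding diary and an OAB-q at the start of their 5th and 8th week of treatment". That makes three measurement occasions.

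The Objectives row is worded more strongly: "To demonstrate safety and effectiveness of nerve stimulation using the Leo-U TranStim System".

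**The concern.** The power figure and the endpoints appear to answer different questions. A repeated measures ANOVA with subjects as their own controls tests whether the mean changes across diaries. The endpoints ask whether a change reaches 50%, 20% or 15%. A mean change can differ clearly from zero and still fall well short of 50%.

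The 0.7 is also hard to interpret. It could be a mean change over the SD of change, a mean change over the raw SD, or Cohen's f, and it could belong to any of three outcomes. One standardized change can match all three thresholds only if the SDs of percentage change stand in the ratio 50:20:15.

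If the objective is read literally, two things could go wrong. A significant ANOVA might be presented as proof of effectiveness when the 50% criterion was missed. The choice between a per-subject and a group reading might be made after the data are seen.

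**Working it through.** **Inputs from the documents.** n = 10, effect size 0.7, alpha 0.05 and target power 0.80 (Sample Size Calculation); three occasions, namely baseline, week 5 and week 8 (Procedures, steps 3 and 5).

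**Assumed, because not stated.** The metric of 0.7, the within-subject correlation ρ, sphericity and, for the paired test, sidedness.

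**Can the stated 80% at n = 10 be reproduced?**

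*Reading A: 0.7 is the mean change over the SD of change, paired comparison.* The noncentrality is 0.7 × √10 = 2.21 on 9 df, against a two-sided critical value of 2.262. Power is 0.51 (one-sided 0.65).

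*Reading B: 0.7 is Cohen's f or a raw-SD difference, repeated measures ANOVA.* The noncentrality is λ = f² × n × m / (1 − ρ), with m occasions and df (m − 1) and (n − 1)(m − 1). A raw-SD difference d on two occasions corresponds to f = d/2 = 0.35. On three occasions, a step to 0.7 that is held (means 0, 0.7, 0.7) has variance 0.98/9 = 0.109, so f = 0.33. A straight-line change (0, 0.35, 0.7) has f = 0.286.

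| Interpretation of 0.7 | m | ρ | λ | Power at n = 10 |
|---|---|---|---|---|
| raw d, f = 0.35 | 2 | 0 | 0.1225 × 20 / 1 = 2.45 | 0.29 |
| raw d, f = 0.35 | 2 | 0.75 | 0.1225 × 20 / 0.25 = 9.8 | 0.80 |
| Cohen's f = 0.7 | 2 | 0 | 0.49 × 20 / 1 = 9.8 | 0.80 |
| raw d, straight line, f = 0.286 | 3 | 0.7 | 8.17 | 0.65 |
| raw d, straight line, f = 0.286 | 3 | 0.8 | 12.25 | 0.83 |
| raw d, step, f = 0.33 | 3 | 0.7 | 0.1089 × 30 / 0.3 = 10.89 | 0.78 |
| raw d, d/2 convention, f = 0.35 | 3 | 0.7 | 0.1225 × 30 / 0.3 = 12.25 | 0.83 |
| Cohen's f = 0.7 | 3 | 0.5 | 0.49 × 30 / 0.5 = 29.4 | 0.996 |

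The 0.29 needs zero correlation between diaries kept by the same woman, which sits badly with an own-control design. The three-occasion rows with raw d match the protocol's schedule, and at correlations of 0.7 to 0.8 they lie on either side of 0.80. So the plan's figure is attainable under ordinary assumptions, although it cannot be traced to one set of them.

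**Does significance imply that a threshold was met?** No. As an illustration, take percentage falls as normal with an assumed SD of 30 points and a true mean fall of 30%. The standardized change is 30/30 = 1.0, and power against zero at n = 10 is 0.80. The standard error of the mean is 30/√10 = 9.49. The chance that the observed mean reaches 50% is P(Z > 20/9.49 = 2.11) = 0.018. The two questions do differ, but the documents do not treat one as the answer to the other.

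**What can 10 subjects say about a threshold?** On a per-subject reading, 5 responders of 10 give an exact 95% interval of 19% to 81%, and 7 of 10 give 35% to 93%. That precision suits a study looking for trends. It would not suit a confirmatory claim, and the Sample Size Calculation row makes none.

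**The case for a change.** The strongest case for acting is that the sponsor chose to add a formal power claim to a feasibility study and set an objective of demonstrating effectiveness. The required wording would be cheap: say what 0.7 means, fix the reading of each threshold, name the diary, and add an interval. Without it, the per-subject or group reading could be picked after the results are known.

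The factual part stands. The 0.7 is not interpretable as written, the reading of the thresholds is open, and the ANOVA alone cannot show that a threshold was reached.

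The harm is less secure:

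- All three endpoints are changes from pre-treatment, so testing for change and then comparing its size with a clinical benchmark is a normal pairing. The test is incomplete for the endpoints, not irrelevant to them.
- No sentence makes ANOVA significance a success criterion. A misleading report would be the author's doing, not the plan's.
- The heading over the efficacy endpoints points to the last diary. Some doubt remains, because that diary is completed at the start of week 8, before treatment ends.
- Alpha, power, effect size, sample size, test and drop-out are all stated. What is missing is limited to the outcome, metric, correlation and sidedness.

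**Conclusion.** No change is needed. The sample-size sentence is under-documented, but it is not shown to be wrong. Power at n = 10 is 0.51 on the paired SD-of-change reading and 0.78 to 0.83 on a raw-SD reading over the three scheduled diaries at correlation 0.7, falling to 0.65 if the change is linear at that same correlation. All of these rest on assumed correlation and sphericity, because the documents give neither.

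The suggested additions would write down unstated inputs, record a choice that remains the sponsor's, and add a caution about interpreting the ANOVA. They would correct no figure and no decision rule, would not replace the method, and would leave enrolment at 11. In a one-site feasibility study whose stated use is to look for trends, an analyst can report the proportion of subjects reaching each threshold, or the mean percentage change with its interval, directly from the endpoints as listed. A later confirmatory trial would need the effect-size definition and threshold reading stated in advance. For this study the omission is a gap that can sensibly be filled at analysis.
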